14.	REFERENCES	45

LIST OF ABBREVIATIONS AND RELEVANT DEFINITIONS

ABR	General Assessment and Registration form (ABR form), the application form that is required for submission to the accredited Ethics Committee; in Dutch: Algemeen Beoordelings- en Registratieformulier (ABR-formulier)
5ASA	5-Aminosalicylate
AE	Adverse Events
AG	Acacia Gum
ANOVA	Analysis of Variance
ASV	Amplicon Sequence Variant
BMI	Body Mass Index
BV	In Dutch: Besloten Vennootschap
CA	Competent Authority
CCMO	Central Committee on Research Involving Human Subjects; in Dutch: Centrale Commissie Mensgebonden Onderzoek
COVID-19	Coronavirus disease 2019
CV	Curriculum Vitae
DNA	Deoxyribonucleic Acid
DSMB	Data Safety Monitoring Board
ELISA	Enzyme-linked Immunosorbent assay
EU	European Union
EudraCT	European drug regulatory affairs Clinical Trials
FDR	False Discovery Rate
FFQ	Food Frequency Questionnaire
FOS	Fructo-OligoSaccharides
GBF	Germinated Barley Foodstuff
GCP	Good Clinical Practice
GDPR	General Data Protection Regulation; in Dutch: Algemene Verordening Gegevensbescherming (AVG)
GG	Guar Gum
GI	Gastro-Intestinal
GMP	Good Manufacturing Practice
GP	General Practitioner
GSRS	Gastrointestinal Symptom Rating Scale
HPLC	High Performance Liquid Chromatography
IB	Investigator's Brochure
IBD	Inflammatory Bowel Disease

ID	Identity Document
IC	Informed Consent
IMP	Investigational Medicinal Product
IMPD	Investigational Medicinal Product Dossier
ISO	International Organization for Standardization
METC	Medical research ethics committee (MREC); in Dutch: medisch-ethische toetsingscommissie (METC)
NSF	National Sanitation Foundation
PCoA	Principle Coordinate Analysis
PERMANOVA	Permutational Multivariate Analysis Of Variance
PHGG	Partially Hydrolyzed Guar Gum
P-SCCAI	Patient Simple Clinical Colitis Activity Index
qPCR	quantitative Polymerase Chain Reaction
QQ	Quantile-Quantile
RNA	Ribonucleic Acid
RS	Resistant Starch
(S)AE	(Serious) Adverse Event
SCFAs	Short Chain Fatty Acids
SD	Standard Deviation
SDL	Security Development Lifecycle
SIBDQ	Short Inflammatory Bowel Disease Questionnaire
SPC	Summary of Product Characteristics; in Dutch: officiële productinformatie IB1-tekst
Sponsor	The sponsor is the party that commissions the organisation or performance of the research, for example a pharmaceutical company, academic hospital, scientific organisation or investigator. A party that provides funding for a study but does not commission it is not regarded as the sponsor, but referred to as a subsidising party.
SUSAR	Suspected Unexpected Serious Adverse Reaction
TNF- α	Tumour Necrosis Factor alpha
UAVG	Dutch Act on Implementation of the General Data Protection Regulation; in Dutch: Uitvoeringswet AVG
UC	Ulcerative Colitis
WMO	Medical Research Involving Human Subjects Act; in Dutch: Wet Medisch-wetenschappelijk Onderzoek met Mensen

SUMMARY

Rationale: Ulcerative colitis (UC) patients respond differently to treatments/interventions (e.g. diet/fecal microbiota transplantation), but the reason for this individual specificity remains unknown. We hypothesize that the baseline fecal microbiota composition determines the efficacy of a treatment/intervention, and potential responders, i.e. patients showing symptoms improvement after treatment, can be predicted based on fecal microbiota composition.

Objective: The primary objective is to validate the prediction that prebiotics intervention boosts butyrate production and thereby induces a higher response (lower mean Patient Simple Clinical Colitis Activity Index (P-SCCAI) score) in mild UC patients with low intestinal Bacteroidetes levels (predicted responders), but not in those with high intestinal Bacteroidetes levels (predicted non-responders) at T = 8 weeks. The secondary objectives are to study the effects of prebiotics intervention on response over time (T = 0, 4, 8, 12 and 60 weeks), mucosal inflammation, gastro-intestinal (GI) complaints, stool consistency, stool frequency, fecal microbiota composition, fecal short-chain fatty acids concentrations, quality of life, medication use, and safety parameters in mild UC patients.

Study design: This study is a four-arm double-blind randomized placebo-controlled parallel trial. It consists of a screening stage in which mild UC patients will be assigned to be predicted responders or predicted non-responders based on their fecal Bacteroidetes levels. Afterwards the predicted responders and non-responders will be assigned to either the prebiotics group (arm 1 and 3) or placebo group (arm 2 and 4).

Study population: Adult subjects aged 18-65 years and body mass index 18-30 kg/m² with mild UC defined by P-SCCAI (3-5 points in a 19-point scale), with at least one relapse in the last two years.

Intervention: An 8-week intervention period with four parallel arms: 1) predicted responders with prebiotics treatment (acacia gum, partially hydrolyzed guar gum, and resistant starch), 2) predicted responders with placebo (maltodextrin and corn starch), 3) predicted non-responders with prebiotics treatment, 4) predicted non-responders with placebo, during which the study participants consume the respective supplement (3 grams, twice daily).

Main study parameters/endpoints: The main parameter is the response (mean P-SCCAI score) between arms at T = 8 weeks. The secondary parameters are the response over time at T = 0, 4, 8, 12, and 60 weeks, mucosal inflammation (fecal calprotectin), gastro-intestinal (GI) complaints, stool consistency, stool frequency, fecal microbiota composition, fecal short-chain fatty acids concentrations, health-related quality of life, medication use, and safety parameters.

Nature and extent of the burden and risks associated with participation, benefit and group relatedness: This study has a relatively low burden for the participants. They have to

consume the commercially available supplement twice daily for eight weeks. Besides, several questionnaires (one long FFQ questionnaire on one occasion, two short ones on five occasions, five short ones on three occasions) have to be completed, which is all possible from home. On five occasions they will collect fecal samples (which will be collected from their homes by us). There are no physical risks for the study participants, although some participants may experience minor bloating complaints at the start of using the prebiotics.

1. INTRODUCTION AND RATIONALE

The incidence and prevalence of ulcerative colitis (UC) are increasing worldwide [1]. It is a disease that causes inflammation extending from rectum to colon, and it is one of the two major types of inflammatory bowel disease (IBD) associated with abdominal pain, bloody diarrhea, and urgency to defecate [2]. Compared with the general population, patients with longstanding UC, regardless of clinical activity, have an increased risk for colorectal cancer [2, 3]. Unfortunately, there is no cure for UC and hence, treatments focus on dampening the severity of symptoms. Besides medical or surgical treatments, about half of patients with UC have mild symptoms in which a dietary recommendation, including increasing dietary fiber intake, could help reduce inflammation [4-6]. Although several successes for inducing remission in UC have been reported with treatments including dietary modification and fecal microbiota transplantation, there is no golden grail treatment for all subjects. Some individuals respond well to a certain treatment strategy while others do not. The reason for these differences between individual responses remains speculative. Therefore, it is important to find biomarkers that enable clinicians to identify patients more likely to respond to specific dietary treatments beforehand, and push them back to remission as fast as possible. As a consequence, most therapeutic approaches of UC start with classifying patients according to the severity of the disease [7].

Diet could extensively affect the environment of human intestine, which harbors trillions of microbes, commonly referred to as the “intestinal microbiota”, and “microbiome” (the collection of microbes and all the genes and functionalities they encode [8]). Numerous studies have suggested that the intestinal microbiota is closely associated with overall human health [9, 10]. More importantly, the human gut microbiome is a rich pool of potential biomarkers that have been previously shown to be associated with disease states including IBD [11, 12]. Microbiome-based stratification strategies of patients groups have been widely employed to guide dietary intervention studies [13]. Recently, a low-fat, high-fiber diet has been found to reduce inflammatory markers and alter the microbiome in patients with mild UC or UC in remission [14]. Another similar study demonstrated that a fiber-based prebiotic resulted in less abdominal pain and cramping in UC patients [15]. This indicates that increasing dietary fiber intake could be beneficial for maintaining periods of remission or improving clinical outcomes in patients with UC. Furthermore, short chain fatty acids (SCFAs) such as butyrate are produced by intestinal bacteria when they break down dietary fibers and these are considered beneficial for gut health. In a pilot study, it was demonstrated that UC patients could take a fiber-rich diet to increase the fecal butyrate level [5]. However, response to a treatment differs drastically between subjects, with some patients entering remission (responder), while others fall or remain into relapse (non-responders). The reasons for this inconsistent response between subjects remain speculative but may be the result of differences in the personal gut microbiota composition [16].

[figure not shown]

Figure 1 Existent tipping point in ecosystem. (adapted from reference 17 and 18.)

Looking from an ecological perspective, ecosystems are generally consisting of alternative stable states that are resilient to (minor) perturbations. Changing from one stable state into another stable state needs a strong perturbation in which a tipping point needs to be crossed (Figure 1) [17, 18]. For example, both deserts and rainforests are stable states, and only a drastic perturbation, like deforestation, allows a rainforest to cross a tipping point to become a desert, and similarly, it will need a lot of effort to have it return again from a desert into a rainforest in

which a tipping point needs to be crossed as well. We believe that similar ecological principles exist for intestinal microbial ecosystems. Recently, we have published a review in which groups of microbiomes containing certain characteristics can be considered as alternative ecosystems states that are generally resilient to perturbations [19]. These stable states can both be homeostatic microbiomes in healthy subjects as well as microbiomes associated with disease, such as UC, and switching from one to the other needs strong perturbations (such as diseases/infections causing diarrhea) or treatments (such as antibiotics use or prebiotic consumption) that result in crossing the tipping point.

Generally, UC patients have a gut microbiota composition that is different from that observed in healthy subjects. In UC patients, alterations of the intestinal microbiome have been observed in many clinical studies, characterized by a general reduction in fecal microbiota diversity, along with phylum-level increases in Bacteroidetes and decreases in Firmicutes, and lower levels of butyrate [20-22]. Nevertheless, there is also a clear subject-specific impact on the gut microbiota composition. For healthy subjects, different alternative healthy states of the gut-microbiome have been identified, and we speculate that different alternative states also exist for UC patients. Indeed a recent study on the rat model for UC has indicated the existence of health states and disease active states [23]. Similarly, alternative intestinal ecosystem states have also been observed in pediatric UC and these could affect remission in UC [24].

[figure not shown]
The Bacteroidetes phylum is one of the most abundant phyla in the human gut microbiome and dramatic differences at this phylum level have been observed [20, 25]. Remarkably, induction of sustained remission via fecal microbiota transplantation was associated with a baseline microbiota that was more similar to that of healthy individuals which have a relatively low Bacteroidetes level (average 5% and 8%, respectively), while non-responders have a relatively high baseline Bacteroidetes level (average 19%) [20]. Moreover, the induction of sustained remission was associated with an improved butyrate production capacity. Hence, we hypothesize that the gut microbiome of UC patients with low intestinal Bacteroidetes levels are characterized as an alternative state that has a tipping point that is

easier to be crossed by an intervention compared to those with higher Bacteroidetes levels. We speculate that crossing this tipping point can be reached by stimulating intestinal butyrate production capacity.

There is a growing recognition that not an individual fiber but a mixture of them are more likely to promote the growth of SCFAs producing bacteria, because individual or consortia of bacteria play different, sometimes complementary, roles in the fiber degradation process. Therefore, by using a fiber mixture, the physiological effects of fiber (e.g., SCFAs production and bowel movement modulation) would be stimulated [26]. To identify a potential treatment targeting the butyrate-producing capacity that could be used in an intervention study, we applied an *in vitro* screening of different dietary fiber mixtures (so-called “butyrate boosters”) on the gut microbiome of UC patients to test our hypothesis. From this pilot study, we identified a promising fiber prototype product (mixture of acacia gum, partially hydrolyzed guar gum, and resistant starch) that boosted butyrogenic activity in microbiota with low Bacteroidetes levels, while it remained unaffected in those with high Bacteroidetes levels (unpublished results). To further test our hypothesis, we will conduct a dietary intervention study with a mixture of butyrate boosting fibers (hereinafter referred to as prebiotics) of which we predict they will induce a higher response in mild UC patients with a low intestinal Bacteroidetes level, while mild UC patients with a high intestinal Bacteroidetes level will be less affected (**Figure 2**).

Figure 2 PREDUCTOME study : hypotheses

2. OBJECTIVES

Primary Objective:

The primary objective is to validate the prediction that prebiotics intervention boosts butyrate production and thereby induces a higher response (lower mean Patient Simple Clinical Colitis Activity Index (P-SCCAI) score) in mild UC patients with low intestinal Bacteroidetes levels (predicted responders), but not in those with high intestinal Bacteroidetes levels (predicted non-responders) at T = 8 weeks

Secondary Objective(s):

1. To study the effects of the prebiotic intervention on response over time at T = 0, 4, 8, 12, and 60 weeks in mild UC patients
2. To study the effects of the prebiotic intervention on mucosal inflammation (fecal calprotectin levels) in mild UC patients
3. To study the effects of the prebiotic intervention on gastro-intestinal (GI) complaints (e.g., indigestion, abdominal pain) in mild UC patients
4. To study the effects of the prebiotic intervention on stool consistency and frequency in mild UC patients
5. To study the effects of the prebiotic intervention on the gut microbiota composition and SCFAs profile in mild UC patients
6. To study the effects of the prebiotic intervention on health-related quality of life in mild UC patients
7. To study the effects of the prebiotic intervention on medication use in mild UC patients
8. To study the effects of the prebiotic intervention on safety parameters in mild UC patients

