4.4 Sample size calculation

The primary objective of the trial is to validate the prediction that a higher response (lower mean P-SCCAI score) is induced at T= 8 weeks by the prebiotics intervention in mild UC patients with low Bacteroidetes levels (predicted responders), but not in those with high Bacteroidetes levels (predicted non-responders) in their gut. Mild UC is defined as a P-SCCAI score of 3 to 5. According to an extensive study regarding UC disease activity conducted in the Netherlands, mild UC patients have a P-SCCAI score of 3.5 ± 0.5 (Mean \pm standard deviation (SD)), and patients in remission score at 1.0 ± 0.33 (Mean \pm SD)[34, 35].

In a series of germinated barley foodstuff (GBF) intervention studies, 10 mild to moderately active UC patients received 30 grams of GBF (equals to 10 grams fiber) daily for 4 weeks [4], and researchers found a significant decrease in clinical activity index scores. In a later study, another group of 11 mildly to moderately active UC patients consuming 20-30 grams of GBF (equals to 6.66-10 g fiber) daily for 4 weeks showed similar results, with decreases in clinical activity index scores [28].

Based on two-sided statistical testing for unpaired continuous data, an $\alpha=0.05$ (chance on type-I error) and $\beta=0.10$ (chance on type-II error), and assuming a 20% difference of mean P-SCCAI score between predicted responders with prebiotics and predicted non-responders with prebiotics, it was calculated that at least 11 subjects per group are needed for the primary outcome P-SCCAI ($\mu_1=3.5$; $SD_1=0.5$; $\mu_2=2.8$). According to previous trials on prebiotics on IBD patients, a 20% of drop-out rate is commonly seen. Given that the intervention duration is 8 weeks long, followed by a 1 year follow-up, higher dropout rate (30%) is expected. To compensate for a 30% drop-out rate, 15 subjects per group are needed.

To reach inclusion of 30 predicted responders and 30 predicted non-responders, we made an estimate how many subjects we need to screen based on the earlier obtained microbial composition of stool samples from UC patients in the Ede area. Around 50% of these subjects were categorized as low Bacteroidetes subjects (predicted responders) and while 17% of them as high Bacteroidetes subjects (predicted non-responders). To include these responders we will need to screen 177 mild UC patients.

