10. STATISTICAL ANALYSIS

Statistical analyses will be done using the statistical program embedded within R. The threshold for significance will be set at $p<0.05$, with a FDR correction for 16S rRNA gene sequence data. In general, the continuous data will be presented as mean \pm standard deviation or mean and interquartile range when skewed, and categorical data as counts and percentages. Normality will be checked by visual inspection and QQ plots, followed by the Shapiro Wilk test for testing if data show a normal distribution.

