10.1 Primary study parameter(s)

Response (mean P-SCCAI score) between arms at T = 8 weeks

To assess the response, data of mean P-SCCAI score within each arm at T = 8 weeks (after the intervention) will be obtained.

Firstly, the mean P-SCCAI score between the predicted responders with prebiotics and predicted non-responders with prebiotics will be compared by using a Student T-test if normally distributed, otherwise a Mann-Whitney U test when skewed.

Secondly, the mean P-SCCAI score between prebiotics and placebo groups within predicted responders or predicted non-responders will be compared by using a Student T-test if normally distributed, otherwise a Mann-Whitney U test when skewed.

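### Within the primary analysis, the 'but not in predicted non-responders' half of the objective could rest only on a non-significant prebiotics v placebo test, which does not show absence of effect

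*Protocol*

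**What the plan says.** The primary objective (Protocol, section 2) has two parts. Prebiotics are to give a higher response, meaning a lower mean P-SCCAI, in mild UC patients with low Bacteroidetes levels, "but not in those with high intestinal Bacteroidetes levels (predicted non-responders) at T = 8 weeks". Section 4.4 restates both parts. Section 1 ends with a weaker prediction: patients with high levels will be less affected.

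Section 10.1 fixes the primary tests. The first compares predicted responders on prebiotics (arm 1) with predicted non-responders on prebiotics (arm 3). In the second, "the mean P-SCCAI score between prebiotics and placebo groups within predicted responders or predicted non-responders will be compared by using a Student T-test", or a Mann-Whitney test if the data are skewed. This covers arm 1 v arm 2 and arm 3 v arm 4. Section 10 sets significance at p<0.05.

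The sample size in section 4.4 is for the first comparison only, "assuming a 20% difference of mean P-SCCAI score between predicted responders with prebiotics and predicted non-responders with prebiotics". It concludes that "at least 11 subjects per group are needed for the primary outcome P-SCCAI" and then that "To compensate for a 30% drop-out rate, 15 subjects per group are needed".

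Section 10.2 adds, as a secondary analysis, a repeated-measures mixed model over weeks 0 to 60 with a treatment by responding by time point term.

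**The concern.** The second half of the objective asserts that an effect is absent. A difference test can contradict such an assertion but cannot establish it, because a non-significant result also arises when a real effect is missed.

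No other primary comparison fills the gap. Arm 1 v arm 3 has no placebo reference, so it cannot isolate the effect of prebiotics in predicted non-responders. The three-way term in section 10.2 is secondary and asks whether effects differ, not whether one of them is absent. That leaves arm 3 v arm 4.

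If non-significance there were taken as validation, smaller or noisier arms would make that half of the objective easier to 'validate'. At stake is a false statement that half the primary prediction has been confirmed.

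**Working it through.** **Inputs.** From section 4.4: means 3.5 and 2.8 (difference 0.7), SD 0.5, two-sided alpha 0.05, power 90%, 11 per group, 15 per group after allowing for 30% drop-out. Completers per arm: 15 × 0.7 = 10.5, about 11. Assumptions not in the protocol: a smaller true benefit of 0.35 (half of 0.7), and week-8 SDs of 0.75, 1.0 and 1.5. All figures below are for the t-test.

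**The protocol's own figure.** n = 2 × [0.5 × (1.960 + 1.282) / 0.7]² = 10.7, so 11 per group. This reproduces by the normal approximation. By the non-central t, 11 per group gives 87.7% power.

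**Precision of arm 3 v arm 4.** Half-width of the 95% CI = t(0.975, 2n−2) × SD × √(2/n).
- 11 per arm, SD 0.5: 2.086 × 0.5 × √(2/11) = 2.086 × 0.2132 = 0.44.
- 15 per arm, SD 0.5: 2.048 × 0.5 × √(2/15) = 2.048 × 0.1826 = 0.37.

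With 11 per arm, a just non-significant estimate lies just under 0.44 in favour of prebiotics. Its interval runs from just below 0 to about 0.44 + 0.44 ≈ 0.89 (unrounded 2 × 0.4447), which includes the planned 0.7.

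**Chance of missing a real benefit.** This is 1 minus the non-central t power, with non-centrality = benefit / (SD × √(2/n)).

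| Completers per arm | SD | True benefit | Power | Missed |
|---|---|---|---|---|
| 11 | 0.5 | 0.70 | 88% | 12% |
| 11 | 0.5 | 0.35 | 35% | 65% |
| 15 | 0.5 | 0.70 | 96% | 4% |
| 15 | 0.5 | 0.35 | 46% | 54% |
| 11 | 0.75 (assumed) | 0.70 | 55% | 45% |
| 11 | 1.0 (assumed) | 0.70 | 35% | 65% |
| 11 | 1.5 (assumed) | 0.70 | 18% | 82% |

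The larger SDs are shown because section 4.4 quotes 0.5 for mild UC patients, defined by scores of 3 to 5. Week-8 scores are not confined to that band, and the protocol gives no week-8 SD.

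**How a margin would behave.** Suppose 'but not' is claimed only when the 95% CI excludes a benefit of 0.7 (11 per arm, SD 0.5).
- True difference 0: the claim is reached 88% of the time, the same calculation as power for 0.7.
- True benefit 0.35: the claim is still reached about 35% of the time, because the distance to the margin is then 0.7 − 0.35 = 0.35.

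**How the differential contrast would behave.** The week-8 treatment-by-stratum contrast has standard error SD × √(4/n) = 0.5 × √(4/11) = 0.302, on 44 − 4 = 40 degrees of freedom. The half-width is 2.021 × 0.302 = 0.61, and power for an interaction of 0.7 is about 62%.

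**The case against.** The strongest reply is that the protocol nowhere says a non-significant arm 3 v arm 4 test confirms the objective. Section 10.1 says only that means are compared, and how a null result is worded is often left to a SAP. This is right as to the text: a reader might infer a stated rule that p>0.05 validates 'but not', and no such rule exists. What remains is that the protocol itself fixes both the objective and the primary tests, and those tests leave no other primary route to the negative half.

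Second, the prediction is largely comparative, the trial is sized on arm 1 v arm 3, and section 10.2 has an interaction term. This supports a differential reading, which section 1 also uses. It does not support absence of effect, which sections 2 and 4.4 state.

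Third, on the protocol's own SD the arm 3 v arm 4 test is not weak against the full planned effect: 12% missed with 11 per arm, 4% with all 15. This stands. The 65% figure belongs to a 0.35 benefit that the protocol does not name as important, and the larger SDs are assumptions.

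Fourth, one might infer that a null result would lead to withholding the product from patients who benefit. The protocol describes a commercially available supplement and links no result to withholding it, so that harm is not supported.

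**Conclusion.** The point holds in a limited form. The objective claims absence of effect, the primary analysis supplies only difference tests, and no criterion connects the two. Taken at section 4.4's SD of 0.5, the main defect is this missing criterion rather than the sample size alone. Sample size becomes decisive for benefits smaller than 0.7, or if the week-8 SD is well above 0.5: at 0.75 to 1.5, a full 0.7 benefit would be missed 45% to 82% of the time. These figures assume the t-test and 11 completers per arm unless stated. The protocol's own wording is also inconsistent, since section 1 predicts a smaller effect and section 2 none. This should be corrected, but it does not invalidate the design.

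**What to change.** In section 10.1, report the arm 3 v arm 4 difference with its 95% CI. State that a non-significant p-value will not be reported as 'no effect' or as validating the 'but not' half. Then choose one of two routes and align sections 1, 2 and 4.4 with it.

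1. Reword the objective to the differential claim in section 1 and assess it by the week-8 treatment-by-stratum contrast with its CI. Given the power of about 62%, present it as an estimate with its interval rather than as a pass-or-fail test.
2. Keep 'but not', and claim it only when the arm 3 v arm 4 interval excludes a margin that the sponsor states and justifies in advance; otherwise report the result as inconclusive. A margin of 0.7 is the largest defensible value, because it equals the whole planned effect. It was set for arm 1 v arm 3, so its use here needs its own justification.

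The change is to wording only, with no added patients, visits or data. The cost is that 'but not' becomes harder to claim. A margin below 0.7 would be harder still to meet.
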